11.7.3 Physical Examinations and Vital Signs

A PE of all body systems and vital signs assessment will be performed at screening and select study visits (see [Table 3-1](#), [Table 3-2](#), [Table 3-3](#), [REDACTED]). At other visits, symptom-directed PEs and symptom-directed vital sign assessments can be performed at the discretion of the investigator or healthcare provider.

A complete PE includes a review of the following systems: head/neck/thyroid; eyes/ears/nose/throat (EENT); respiratory; cardiovascular; lymph nodes; abdomen; skin; musculoskeletal; and neurological. Breast, anorectal, and genital examinations will be performed when medically indicated. After screening, any clinically significant abnormal findings in PEs will be reported as AEs.

The abbreviated PE will include an assessment of the following body systems: EENT, cardiovascular system, respiratory system, abdomen, and skin.

Vital signs include blood pressure (systolic and diastolic), temperature (oral), pulse rate, and respiration rate. These will be assessed following at least a 5-minute rest in the seated position.

11.7.4 Pulse Oximetry

Arterial oxygen saturation by pulse oximetry will be measured at visits specified in [Table 3-1](#) (Part 1 Cohort 1A), [Table 3-2](#) (Part 1 Cohort 1B), [Table 3-3](#) (Part 2), [REDACTED]. This will be assessed following at least a 5-minute rest (seated) and before study drug dosing. At visits when study drug is taken at the site, pulse oximetry will be collected before the morning dose. This is a noninvasive measure of oxygen delivery to the tissues and has been correlated with clinical status and lung function.

11.7.5 Electrocardiograms

Standard 12-lead ECGs will be performed using a machine with printout according to the Schedule of Assessments ([Table 3-1](#) [Part 1 Cohort 1A], [Table 3-2](#) [Part 1 Cohort 1B], [Table 3-3](#) [Part 2], [REDACTED]). Additional standard 12-lead ECGs will be performed at any other time if clinically indicated.

The subject will be instructed to rest in the seated position for at least 5 minutes before having an ECG performed.

The ECG traces will be manually read at the study site at the Screening Visit and Safety Follow-up Visit. A printout of the ECG traces will be made for safety review by the investigator and maintained with source documentation. Clinically significant ECG abnormalities occurring during the study through the Safety Follow-up Visit will be recorded as AEs.

To ensure safety of the subjects, a qualified individual at the study site will make comparisons to baseline measurements. If the QTcF is increased by >45 msec from the baseline or an absolute QTcF value is ≥ 500 msec for any scheduled ECG, 2 additional ECGs will be performed approximately 2 to 4 minutes apart to confirm the original measurement. If either of the QTcF values from these repeated ECGs remains above the threshold value (>45 msec from baseline or ≥ 500 msec), a single ECG will be repeated at least hourly until QTcF values from 2 successive ECGs fall below the threshold value that triggered the repeat measurement. Further details pertaining to ECGs will be provided to sites in a separate document (ECG Manual).

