10.4 Study Drug Interruption and Stopping Rules

Subjects with new treatment-emergent ALT or AST elevations of $>3 \times \text{ULN}$, or total bilirubin $>2 \times \text{ULN}$, must be followed closely, including confirmatory testing performed by the central laboratory within 48 to 72 hours of the initial finding and subsequent close monitoring of ALT, AST, and bilirubin levels, as clinically indicated.

If a subject cannot return to the site for confirmatory testing, a local laboratory may be used. Local laboratory results must be reported immediately to the medical monitor, and the subject must have the tests repeated and sent to the central laboratory as soon as possible (ideally within 48 to 72 hours).

Study drug administration **must be interrupted** immediately (prior to confirmatory testing), and the medical monitor must be notified, if any of the following criteria are met:

- ALT or AST $>8 \times \text{ULN}$
- ALT or AST $>5 \times \text{ULN}$ for more than 2 weeks

- ALT or AST $>3 \times$ ULN, in association with total bilirubin $>2 \times$ ULN and/or clinical jaundice
- Indirect bilirubin $>2 \times$ ULN (defined as ULN for total bilirubin minus ULN for direct bilirubin)

A thorough investigation of potential causes should be conducted, and the subject should be followed closely for clinical progression.

Study drug administration **must be discontinued**, if either of the following criteria is met:

- Subsequent ALT or AST values confirm the initial elevation that satisfied the interruption rule (above), and no convincing alternative etiology (e.g., acetaminophen use, viral hepatitis, or alcohol ingestion) is identified, regardless of whether transaminase levels have improved
- Indirect bilirubin $>2 \times$ ULN (defined as ULN for total bilirubin minus ULN for direct bilirubin), in association with decreased haptoglobin

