12.3.5.3 Electrocardiogram

For the treatment-emergent ECG measurements, a summary of observed values and change from baseline values will be provided overall and by treatment group for each Part, at each scheduled visit and time point, as applicable, for the following ECG interval measurements (in ms): RR, PR, QT, and QT corrected for HR (QTcF), QRS duration, and HR (beats per minute).

The number and percentage of subjects meeting a threshold analysis criterion during the TE Period will be summarized overall and by treatment group. The threshold analysis criteria will be provided in the SAP.

Additional ECG analyses will be described in the SAP.

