## Appendix B: Analysis Visit Windows for Safety and Efficacy Assessments

Table 11-5 Analysis Visit Windows for Safety and Efficacy Assessments			
Assessment	Visita	Target Study Dayb	Analysis Visit Window (in study days)
Safety Assessment (Part 1, Cohort 1A)			
Serum Chemistry Hematology Urinalysis Vital Signs (including Weight)	Day 1 (Baseline)	1	≤1 Pre-dose
	Day 8	8	[1, 12]
	Day 15	15	(12,22]
	Day 29	29	(22, 36]
	Day 43	43	(36, 50]
	Safety Follow-up	57	Use nominal visit
Coagulation	Day 1 (Baseline)	1	≤1 Pre-dose
	Day 15	15	[1, 22]
	Day 29	29	(22, 43]
	Safety Follow-up	57	Use nominal visit
Standard 12-Lead ECG	Day 1 (Baseline; before dosing)	1	Use nominal visit for all visits
	Day 1 (4 hours after dosing)	1	
	Day 8	8	
	Day 15 (before dosing and 4 hours after dosing)	15	
	Day 29	29	
	Day 43	43	
	Safety Follow-up	57	
Safety Assessment (Part 1, Cohort 1B)			
Serum Chemistry Hematology Urinalysis Vital Signs (including Weight)	Day 1 (Baseline)	1	≤1 Pre-dose
	Day 15	15	[1,22]
	Day 29	29	(22, 36]
	Day 43	43	(36, 50]
	Safety Follow-up	57	Use nominal visit
Coagulation	Day 1 (Baseline)	1	≤1 Pre-dose
	Day 15	15	[1,22]
	Day 29	29	(22, 43]
	Safety Follow-up	57	Use nominal visit
Standard 12-Lead ECG	Day 1 (Baseline; before dosing)	1	Use nominal visit for all visits
	Day 1 (4 hours after dosing)	1	
	Day 15 (before dosing and 4 hours after dosing)	15	
	Day 29	29	
	Day 43	43	
	Safety Follow-up	57	
Safety Assessment (Part 2)			

a Visit name is used to report data in tables, listings and figures.

b Target day time point per protocol is pre-dose, except for ECG measurements.

Table 11-5 Analysis Visit Windows for Safety and Efficacy Assessments			
Assessment	Visita	Target Study Dayb	Analysis Visit Window (in study days)
Serum Chemistry Hematology Urinalysis Vital Signs (including Weight)	Day 1 (Baseline)	1	≤1 Pre-dose
	Day 15	15	[1,22]
	Day 29	29	(22, 36]
	Day 43	43	(36, 50]
	Day 57	57	(50, 71]
	Safety Follow-up	85	Use nominal visit
Coagulation	Day 1 (Baseline)	1	≤1 Pre-dose
	Day 15	15	[1,22]
	Day 29	29	(22, 57]
	Safety Follow-up	85	Use nominal visit
Standard 12-Lead ECG	Day 1 (Baseline; before dosing)	1	Use nominal visit for all visits
	Day 1 (4 hours after dosing)	1	
	Day 15 (before dosing and 4 hours after dosing)	15	
	Day 29	29	
	Day 43	43	
	Day 57	57	
	Safety Follow-up	85	

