
Notes:
 
The analysis visit windows will be applied using the following rules for both scheduled and unscheduled visits:
 
 
1. If no numerical measurement is available within a visit window, the measurement will be considered missing for the visit.
 
2. If there is more than 1 numerical measurement available within the same visit window, use the following rules:                         
 
a. For efficacy parameters: if there are multiple measurements within a visit window, the measurement at the scheduled visit will be used. Otherwise,                                 
 
i. If there are no measurements at the scheduled visit, then the measurement closest to the target day will be used; or
 
ii. If there are multiple measurements with the same distance to the target day, the latest measurement will be used.
 
 
 
b. For safety parameters: if there are multiple measurements within a visit window,                                 
 
i. The measurement closest to the target day will be used; or
 
ii. If there are multiple measurements within the same distance from the target day, the latest measurement will be used.
 
iii. For tables of the extreme lab measurement based on ULN or LLN, convert the lab measurements into times of ULN or LLN first, and then select the extreme measurement.
 
 
 
 
 
			

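### SAP Appendix B has no scheduled-first rule for safety data, so a liver retest, and possibly a repeat ECG, taken because a value was abnormal can replace that value in the by-visit summaries

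*Protocol*

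**What the plan says.** **Repeat ECGs.** Protocol 11.7.5 sets the trigger: "If the QTcF is increased by >45 msec from the baseline or an absolute QTcF value is ≥ 500 msec for any scheduled ECG". Then "2 additional ECGs will be performed approximately 2 to 4 minutes apart to confirm the original measurement". If either of these is still over the threshold, "a single ECG will be repeated at least hourly until QTcF values from 2 successive ECGs fall below the threshold value" that set off the repeats.

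**Liver retests.** Protocol 10.4 requires, for new ALT or AST above 3 × ULN or total bilirubin above 2 × ULN, "confirmatory testing performed by the central laboratory within 48 to 72 hours of the initial finding".

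**Choice of one value per visit.** SAP Appendix B, notes to Table 11-5, covers scheduled and unscheduled visits alike. For efficacy (rule 2a), "if there are multiple measurements within a visit window, the measurement at the scheduled visit will be used". For safety (rule 2b), the value closest to the target day is taken, and then: "If there are multiple measurements within the same distance from the target day, the latest measurement will be used". Rule 2b has no step that prefers the scheduled measurement.

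**Assignment to visits.** Table 11-5 gives chemistry study-day windows. For 12-lead ECG, in every cohort and part, it says "Use nominal visit for all visits". SAP 8.1 lets unscheduled values into scheduled visits through the windowing rules, and also into maximum and minimum on-treatment values.

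**Tables affected.** Protocol 12.3.5.3 plans the ECG tables by scheduled visit and time point: "a summary of observed values and change from baseline values will be provided overall and by treatment group for each Part". SAP 8.4.2 and 8.4.3 plan by-visit summaries of laboratory and ECG values. Separately, they count subjects who meet a threshold at any time in the treatment-emergent period.

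**The concern.** Liver retests and repeat ECGs are taken only because a value was abnormal. A selection rule that can prefer them over the scheduled value makes the tabulated figure depend on the outcome. For ECG the series also stops only after values are back under the trigger, so where the last one is used the replacement goes one way.

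ECGs and laboratory values are part of the primary safety endpoint, and the arms are small (6 to 18 subjects by the planned numbers). If the substitution occurs, the by-visit mean, maximum and change from baseline describe a different measurement for affected subjects than for everyone else at that visit. An arm with a real QTcF effect could look closer to its comparator in those summaries than it is.

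**Working it through.** The plan states no figure on this point, so the check traces the rules and then does simple arithmetic.

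**1. Liver tests: which sample does rule 2b choose?**

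Inputs: target Day 15 with visits allowed on Days 13 to 17 (schedules of assessments); chemistry windows for Day 15 of (12, 22] in Cohort 1A and [1, 22] in Cohort 1B and Part 2 (Table 11-5). The retest is assumed to fall 2 to 4 days after the visit. The protocol counts 48 to 72 hours from when the abnormality is found, which may be a day after the sample. The retest is chosen when |retest day − 15| ≤ |visit day − 15|, because a tie goes to the later sample.

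| Visit day | Distance | Retest days (distance) | Retest chosen on |
|---|---|---|---|
| 13 | 2 | 15 (0), 16 (1), 17 (2) | 15, 16, 17 |
| 14 | 1 | 16 (1), 17 (2), 18 (3) | 16 |
| 15 | 0 | 17 (2), 18 (3), 19 (4) | none |
| 16 | 1 | 18 (3), 19 (4), 20 (5) | none |
| 17 | 2 | 19 (4), 20 (5), 21 (6) | none |

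Day 29 has the same pattern (27 with 29, 30 or 31; 28 with 30). At Cohort 1A Day 8 the only case is 7 with 9. No assumption about visit labels is needed, because unscheduled chemistry values enter the day windows. The direction is not fixed, since a retest can be higher or lower. Where the interruption rules in Protocol 10.4 apply, study drug is stopped before confirmatory testing, so the substituted value may be off drug.

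Shift in the arm mean = (retest − scheduled)/n for one affected subject: 16.7% of the difference at n=6, 12.5% at n=8, 6.3% at n=16, 5.6% at n=18.

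**2. ECG: two branches**

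Take assumed QTcF changes of +52 (scheduled), +50 and +48 (confirmatory), +44 and +40 (hourly). The last two are both below +45, so the series ends.

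- *Repeats labelled with the same nominal visit and time point.* All five tie on day, so rule 2b takes +40 and the by-visit summary loses +52.
- *Repeats labelled as unscheduled.* Nominal-visit assignment keeps +52 and nothing is replaced.
- *Either way,* the maximum on-treatment change is +52.

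**3. Size in the first ECG branch**

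Arm sizes from planned N and ratios: TC-1A 10 × 4/5 = 8; TC-1B-low 32 × 1/4 = 8; TC-1B-high 32 × 2/4 = 16; TC-2 24 × 3/4 = 18; TEZ/IVA 24 × 1/4 = 6. Shift in the arm mean per affected subject = fall/n. The falls are assumptions.

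| n | Fall 5 msec | Fall 15 msec | Fall 30 msec |
|---|---|---|---|
| 6 | 0.8 | 2.5 | 5.0 |
| 8 | 0.6 | 1.9 | 3.8 |
| 16 | 0.3 | 0.9 | 1.9 |
| 18 | 0.3 | 0.8 | 1.7 |

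A simulation of the 11.7.5 sequence shows the shape only. It assumes a between-subject SD of 14 msec, single-ECG noise of 10 msec, a fade of 2 to 5 msec per hour, and every repeat labelled with the visit. True mean changes of 0, 10, 20 and 30 msec are then tabulated as about −0.1, 9.5, 18.4 and 25.8 msec. The shortfall is negligible without a drug effect and grows with it. None of those inputs is in the documents.

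**The case against.** The strongest objection is that ECGs do not use day windows. Table 11-5 assigns them by nominal visit, the summaries are by scheduled visit and time point, and 11.7.5 itself separates the scheduled ECG from the additional ones. A natural reading keeps the scheduled ECG. The deciding convention may be in the ECG Manual or the internal programming rules, which the documents cite but do not include. This stands: for ECG the bias is conditional. It does not remove the gap, because nominal assignment says which visit an ECG belongs to. When several share a visit and time point, rule 2b is the only visible rule that picks one.

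Second, the safety signal survives elsewhere. Maxima, threshold counts and listings use all values, clinically significant ECG abnormalities are recorded as AEs, and the safety analysis is descriptive. This also stands and limits the consequence to by-visit descriptive summaries. A difference between a by-visit table and an on-treatment maximum is not in itself a contradiction.

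Third, the liver case needs an early visit, and a retest is not repeated until normal. Both are true. The one-way argument therefore does not carry over to liver tests, but selection on the outcome does.

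A reader might infer that copying rule 2a into the safety rules would be enough. For ECG it would not. In the one branch where replacement happens, the repeats carry the scheduled visit label themselves, so a preference for the scheduled visit cannot separate them from the triggering ECG.

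**Conclusion.** The point holds as a defect in a stated selection rule, confined to by-visit descriptive safety summaries. For liver tests, substitution follows directly from the text when a visit is early, with no fixed direction and a shift of 1/n of the difference between samples. For ECG it depends on how repeats are labelled. If they share the nominal visit and time point, one affected subject with an assumed fall of 5 to 30 msec lowers the arm mean by 0.3 to 5.0 msec across arms of 18 to 6. If they are unscheduled, the effect is zero.

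A reader might conclude that the by-visit QTcF tables will show recovered values, or that the plan hides QTc prolongation. The documents support neither. They do not say how repeats are labelled, and every prolonged value still reaches the threshold counts, the maxima and the listings. The simulated figures are illustrations under assumed inputs, not estimates for this trial.

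**What to change.** Add two statements to the Appendix B notes.

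1. For by-visit summaries of safety parameters, use the scheduled measurement first. Apply closest-then-latest only when no scheduled value exists for that visit.
2. For ECG, the originally scheduled pre-dose or 4-hour ECG represents its visit and time point. Repeats under Protocol 11.7.5 are never substituted for it, whatever visit label they carry.

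Keep all repeats and retests in the maxima and minima, the threshold tables and the listings.

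The cost is a small programming change, with no new data. By-visit figures may look slightly less favourable. No change to clinical ECG or liver monitoring is implied. Under SAP section 3, the natural time is before the data cut for the first interim analysis.

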11.7.6 Ophthalmologic Examination

Subjects will undergo an ophthalmologic examination performed by a licensed ophthalmologist or optometrist as noted in Table 3-1, Table 3-2, Table 3-3, [REDACTED] which includes

- measurement of best corrected distance visual acuity of each eye; and
- pharmacologically dilated examination of the lens with a slit lamp.

The screening ophthalmologic examination must be completed and the results reviewed before randomization. This examination does not have to be performed if there is documentation of an examination that met protocol criteria and was within 3 months before the date of informed consent (or assent, when applicable) or if there is documentation of bilateral lens removal for the subject.

If a cataract or lens opacity is identified and determined to be clinically significant by the ophthalmologist or optometrist at the screening examination, the subject must not be randomized. If a cataract or lens opacity is identified and determined to be clinically significant by the ophthalmologist or optometrist after dosing, the subject will be notified. After discussion with the principal investigator and in collaboration with the medical monitor, the subject may elect to continue or discontinue study drug treatment. If the subject discontinues study drug treatment, the subject should complete the ETT and Safety Follow-up Visit. If the subject continues study drug treatment, more frequent ophthalmologic monitoring should be considered.

Additional ophthalmologic examinations may be conducted at the discretion of the investigator. The medical monitor should be notified of any additional ophthalmologic examinations and their results.

In addition, at screening, the following history will be obtained and documented for all subjects:

- history of steroid use
- history of trauma to the eye
- any family history of glaucoma, congenital cataracts, or cataracts arising later in life

11.7.7 Contraception and Pregnancy

The effects of VX-440 monotherapy or in dual or triple combination with TEZ and IVA on conception, pregnancy, and lactation in humans are not known. VX-440, TEZ, and IVA did not show genotoxic potential in a standard battery of in vitro (Ames test, Chinese hamster ovary cell chromosomal aberration) and in vivo (mouse micronucleus) studies. TEZ and IVA were each found to be nonteratogenic in embryo-fetal developmental toxicity studies in rats and rabbits.^{11,12}

In the embryo-fetal developmental toxicity studies, VX-440 was found to be nonteratogenic in rats; however, it demonstrated teratogenicity in rabbits.^{9,23}

Based on these findings and following the recommendations outlined by the Heads of Medicines Agencies Clinical Trial Facilitation Group,²⁴ male subjects with female partners of childbearing potential must use a condom to avoid exposure of a potential embryo or fetus to study drug via the seminal fluid. Female subjects who are of childbearing potential will be required to use highly effective methods of contraception with low user dependency. Based on the potential for CYP induction by VX-440, hormonal methods of contraception will not be considered acceptable methods for female subjects of childbearing potential. Pregnancy testing will be performed at monthly intervals.

11.7.7.1 Contraception

Study participation requires compliance with the contraceptive requirements outlined in Table 11-3.

Table 11-3 Contraceptive Requirements

Male subjects^a	
 • A male subject with a female partner of childbearing potential^b must use a condom to avoid exposure of a potential embryo or fetus to study drug via the seminal fluid. This is required during the period starting from the first dose of study drug until 7 days after the last dose of study drug.
Female subjects^c	
At least 1 of the following methods must be used:
 
 • Continuous use of a non-hormone-releasing intrauterine device for at least 90 days before the first dose of study drug, and until 7 days after the last dose of study drug • Bilateral tubal occlusion (e.g., ligation) in place at least 6 months before the first dose of study drug • Postmenopausal state (defined as amenorrheic for at least 12 consecutive months and a serum FSH level within the laboratory's reference range for postmenopausal females) • Documented hysterectomy or bilateral oophorectomy/salpingo-oophorectomy • Male partner is infertile (e.g., bilateral orchiectomy) • Male partner has vasectomy at least 6 months before the first dose of study drug, with a documented negative postvasectomy semen analysis for sperm

^a In addition to the male condom, other methods of contraception may be used by male subjects and their female partners of childbearing potential, with the exception of female condom due to risk of tearing.

^b Female partners of nonchildbearing potential must either be postmenopausal (defined as amenorrheic for at least 12 consecutive months) or have had a hysterectomy or bilateral oophorectomy/salpingo-oophorectomy.

^c Hormonal contraceptives are not considered an acceptable method for female study subjects because of the potential for a drug-drug interaction with VX-440 resulting in reduced exposure and contraception failure; however, female subjects are not required to discontinue their use of hormonal contraceptives as long as they agree to use at least 1 of the methods listed above.

Additional notes:

- During the course of the study, if a change in a female subject's sexual partner leads to inability to comply with the requirements outlined in Table 11-3, the subject must immediately discontinue study drug and not engage in sexual intercourse with the new partner until 7 days after the last dose of study drug.

- Male subjects must not donate sperm during the period starting from the first dose of study drug until 7 days after the last dose of study drug.
- Female subjects should not nurse a child during the period starting from the first dose of study drug until 7 days after the last dose of study drug.

